Given the described safety profile of sustained release dexamphetamine sulfate preparations, the few (serious) adverse events and mild and often transient adverse reactions observed in studies in stimulant dependent patients, and since the patients in the present study will be thoroughly screened (medical screening, including blood pallet and ECG at baseline and 12 weeks follow-up) and monitored ((S)AEs weekly; heart rate and blood pressure weekly), with medication intake under direct supervision of the treatment centers' medical staff, safety risks are expected to be small and manageable.

Placebo

For the purpose of the present study, the placebo tablets were manufactured by the Slotervaart pharmacist (group of [name]), in compliance with the principles and guidelines of good manufacturing practice (see appendix: IMP-dossier, July 2013). The placebo tablets are identical in shape, color, and content to the sustained release dexamphetamine tablets, with the exception of the active ingredient – dexamphetamine sulfate – which is replaced by an equal amount of lactose monohydrate in the placebo tablets.

Drug accountability

Study medication will be supplied by the central pharmacy to the local treatment centers. Upon receipt, the local treatment center will store the study medication in a safe. Each study center will keep full record per patient of the study medication dispensed on a daily basis. These records will be periodically checked by independent monitors from the AMC hospital pharmacy. The study medication has to be taken under supervision of the treatment staff at the treatment site. Any unused study medication must be accounted for, and documented, by the local treatment center, and will be desctructed according to the procedures developed by the AMC hospital pharmacy.

ASSESSMENTS

In both the control and experimental group, study assessments will take place at baseline, and 4, 8, and 12 weeks after baseline (see Table 1. Overview of assessments and instruments). The assessments will be conducted by trained research-assistants who are independent from the treatment staff, using standardized instruments to minimize information bias. At baseline, the treating physician will conduct a thorough medical examination to determine whether the patient should be excluded from the study due to the presence of contraindications.

At baseline, the following self-report instruments will be administered: the Composite International Diagnostic Interview Substance Abuse Module (CIDI-SAM; cocaine and alcohol dependence; Cottler, 2000), as well as questions on suicidal risk from the MINI International Neuropsychiatric Interview (MINI; Sheehan et al., 1998); the short version of the Addiction Severity Index (ASI; McLellan et al., 1980, 1992; Hendriks et al., 1989), supplemented with questions about current illegal activities, income, and living arrangements (similar to the ASI-version used in the CRF of the Dutch RCT on medically prescribed heroin); the Time Line Follow-Back (TLFB, pertaining to cocaine use in the previous month; Sobell & Sobell, 1992); the Maudsley Addiction Profile-Health Symptoms Scale (MAP-HSS; Marsden et al., 1998); the Symptoms Check List-90 (SCL-90; Derogatis et al., 1993; Arrindel & Ettema, 1996); the Obsessive Compulsive Drug use Scale (OCDS; Anton et al., 1996; De Wildt et al., 2005), the EuroQol (EQ-5D; Brooks, 1996), and the Readiness to Change Questionnaire (RCQ; Defuentes-Merillas et al., 2002).

At the 12 weeks assessment, (follow-up versions of) each of these instruments will be administered again, with the exception of the CIDI, MINI and RCQ. In addition, patient satisfaction (Client Satisfaction Questionnaire; CSQ-8; De Wilde & Hendriks, 2005), supplemented with questions pertaining to the received medication (placebo or sustained release dexamphetamine) will be assessed.

At the 4 and 8 weeks assessment, the TLFB (pertaining to cocaine use in the previous month) and the ASI-items pertaining to other substance use will be administered, as well as the MAP-HSS, SCL-90, OCDS, and EQ-5D.

Additional assessments include blood sampling (laboratory screen: BSE, MCH, MCV, MCHC, GGT, ALAT, ASAT, alkalase phosphate, leucocytes, thrombocytes) (screening/baseline assessment and 12 weeks assessment; 2 x 16 ml), ECG (screening/baseline assessment and 12 weeks assessment), weekly medical screening; weekly check on heart rate and blood pressure during the entire study period; two times/week urine sampling (cocaine metabolites) during the 4 weeks preceding the 12 weeks assessment; monthly pregnancy testing (females); weekly registration of adverse events, serious adverse events (see: Safety reporting), and co-medication; study drug accountability (placebo and sustained release dexamphetamine); treatment compliance.

OUTCOME MEASURES AND DATA ANALYSIS

The study data will be analyzed following an intent-to-treat (ITT) approach. The ITT-population consists of all randomized patients who received at least one dose of the prescribed medication. The end of the trial is defined as the last visit of the last patient undergoing the trial. Effect of the intervention will be evaluated in terms of potential efficacy – cocaine use (self-report; urinalyses) and craving for cocaine, use of other substances, physical and mental health, social functioning (including criminality) – as well as in terms of acceptance, medication compliance, safety, and patient satisfaction.

The primary outcome measure pertains to cocaine use, defined as the total number of days of crack-cocaine use during the 12 weeks study period (range: 0 – 84 days), and will be analyzed in a multivariate regression analysis, controlling for study group and treatment site interactions. Secondary effects of the interventions will be evaluated in terms of additional cocaine use related outcome measures (e.g., longest duration of cocaine abstinence, and the number of days cocaine abstinence as well as the mean proportion of cocaine metabolite-free urine samples in the four weeks preceding the week 12 assessment), cocaine craving, use of other substances (self-report), physical and mental health, social functioning (including criminality), and patient satisfaction. Depending on the measurement level of the secondary outcome measure, differences between the two study groups will be analyzed using 2 (time) x 2 (group) repeated measures ANOVA, multivariate (logistic) regression analyses, and GEE-modelling.

Concerning missing data, multiple imputation will be applied for missing interview data. Missing urine samples (two samples/week in weeks 9 to 12) will be considered cocaine-positive.

Since the medication will be dispensed on a daily basis and medication intake will be supervised, compliance with the study medication can be registered reliably on a daily basis. Differences between the study groups (dexamphetamine *versus* placebo) will be described and analyzed in terms of the total number of days in which the medication was taken during the 12 weeks study period, the number of consecutive weeks in which patients were fully compliant (i.e., daily medication intake), and medication intake in the four weeks preceding the week 12 assessment.

Emergency unblinding

Unblinding may be necessary in case of a medical emergency in individual study participants. In case of emergency unblinding, unblinding of the treatment allocation code for individual patients and the reason(s) for unblinding will be fully documented in the study data file and statistical report. In order to be able to distinguish between blinded and unblinded subjects and related assessments in the analyses, each patient's Case Report Form (CRF) will include a code which specifies whether emergency unblinding occurred, as well as the date of unblinding.

Following emergency unblinding, the study treatment will be terminated in all unblinded cases, irrespective of their treatment allocation. These unblinded subjects will, however, be asked to continue their participation in the remaining study assessments, and will remain part of the ITT-analysis. In the ITT-analysis, the observed values of the primary outcome measure (days of crack-cocaine use) during these remaining assessments (after unblinding) of these unblinded patients will be replaced by imputed values based on the patient's baseline value on the primary outcome measure. In subsequent exploratory analyses, we will investigate whether the primary outcome of the trial based on these imputed values differs from the outcome based on the observed values in the unblinded assessments.

Following this approach, selective drop-out from the study will not occur. Unblinding will result in early study treatment termination, but this is not essentially different from other cases of early study treatment termination in which unblinding was not deemed necessary or relevant.

As argued before, based on the low incidence of (S)AEs in previous studies with sustained release dexamphetamine sulfate, the safety risks are expected to be small and the need for emergency unblinding is expected to be low, but will nevertheless be closely monitored during the trial.

POWER CONSIDERATIONS

In the primary analysis, treatment effect will be investigated by means of a multivariate regression model with the total number of days of crack-cocaine use during the 12 weeks (84 days) study period as primary outcome measure (see above). The difference between the sustained release dexamphetamine and placebo study groups in total number of days of crack-cocaine use during 12 weeks treatment, is estimated to be 10 days, with a pooled standard deviation of 17 days (i.e., moderate effect size). Given the feasibility character of the study, the sample size should preferably be limited. As in the parallel studies of topiramate and modafinil ("New pharmacotherapeutic treatment options for crack-cocaine dependent people in the Netherlands"; NL22193.018.09; MEC09/197) we, therefore, have chosen for a lenient alpha of 0.10 to minimize loss of statistical power due to small sample size, instead of the usual 5% false-positive rate, which would be more appropriate for a future confirmatory trial. Given the two-sided alpha=0.10, and a 1-beta power of 0.80, n=36 patients are required in each study group (2x36=72 patients for the present study) (Pocock, 1983; Cohen, 1988).

SAFETY MONITORING AND REPORTING

Adverse events and adverse reactions

Adverse events (AEs) are defined as any undesirable medical experience occurring to a study subject during the study. All AEs reported spontaneously by the subject or observed by the treating physician or his staff will be registered on a weekly basis by the treating physician, defining the relationship of each AE with the study medication (definitely not, possibly, probably, certainly, unknown), and its severity. The severity of AEs will be recorded as follows:

- mild: the AE is transient and easily tolerated;
- moderate: the AE causes the subject discomfort and interrupts the subject's usual activities;
- severe: the AE causes considerable interference with the subject's usual activities and may be incapacitating or life-threatening.

All AEs will be followed until they have abated, or until a stable situation has been reached.

Adverse reactions (ARs) are defined as all undesirable responses to the study medication related to any dose administered.

Unexpected adverse reactions are adverse reactions, of which the nature or severity is not consistent with the side effects (adverse reactions) of sustained release dexamphetamine sulfate described above.

Serious adverse events and unexpected serious adverse reactions

Serious adverse events (SAEs) are defined as any undesirable medical experience or effect occurring to a study subject during the study that at any dose:

- results in death;
- is life-threatening;
- results in persistent or significant disability or incapacity;
- requires hospitalisation or prolongation of hospitalisation;
- is a congenital anomaly or birth defect.

All SAEs will be registered on a weekly basis – or earlier, when observed – by the treating physician, defining the relationship of each SAE with the study medication (definitely not, possibly, probably,

certainly, unknown). All SAEs will be followed until they have abated, or until a stable situation has been reached.

Suspected unexpected serious adverse reactions (SUSARs) are defined as SAEs that are both unexpected (i.e. not consistent with the side effects (adverse reactions) of sustained release dexamphetamine sulfate described above), and at least possibly related to the study medication.

Reporting

- An annual safety report will be submitted to the MEC of the AMC and the Medicine Evaluation Board via ToetsingOnline, consisting of:
 - a list of all SAEs;
 - a list of all (expected or unexpected) serious adverse reactions, and a summary table of these serious adverse reactions, ordered by organ system;
 - an analysis of the safety of the study subjects, including an evaluation of the balance between the efficacy and the harmfulness of the study medication.
- All SUSARs that have arisen during the study will be reported expedited (i.e. within 15 days after the first knowledge of the SUSAR, or within 7 days [preliminary report] in case of a fatal or life-threatening SUSAR) to the MEC of the AMC and to the Medicine Evaluation Board.

ETHICAL CONSIDERATIONS

The study will be conducted under the provisions of the Declaration of Helsinki, as amended in Seoul (2008). The study protocol will be submitted to the Medical Ethics Committee of the Academic Medical Center in Amsterdam, and will not start before formal approval is obtained.

Patients participating in heroin-assisted treatment, with clinically relevant comorbid cocaine use (see inclusion criteria) will be informed about the study and its procedures by means of a written patient information form, and will receive oral explanation about the study by a trained research assistant. Patients will be asked to provide written informed consent by the treating physician before the baseline screening, and have approximately 2 weeks time to consider their decision. Subjects will be informed that they are free to leave the study at any moment, and that this will have no consequences for their ongoing participation in the underlying heroin-assisted treatment.

The investigators will ensure that the subject's anonymity will be maintained. All study data will be treated confidentially and processed anonymously. Each subject will receive a unique identification number, which does not contain initials or date of birth. The CRF and other study documents will only identify subjects by their unique identification number. These identification numbers will be linked with the name of the subject on only one location. This linked file will be kept in a safe, which can only be accessed by the principal investigators.

Patients will receive remuneration for their participation in the study assessments (baseline assessment: 10 euro; 4 weeks assessment: 10 euro; 8 weeks assessment: 10 euro; 12 weeks assessment: 15 euro). In addition, patients will receive 5 euro for each urine sample provided during the 4 weeks preceding the 12 weeks assessment (max. total remuneration: 85 euro).

All patients will be insured for their participation in the study in accordance with legal requirements of article 7 of the WMO.

STUDY PHASES

The duration of the study is 12 months. Month 1: preparation of the study; month 2-5: recruitment of patients in a prevalent sample of crack-cocaine using patients in daily supervised heroin-assisted treatment; month 2-8: execution of the pharmacotherapeutic treatment intervention and related assessments; month 9-12: analyses, reporting, and dissemination.

References

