³ Blood pressure and heart rate will be assessed weekly during the entire study period of 12 weeks.

•••• Indicates weekly (instead of monthly) registration.

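### The follow-up TLFB looks back a fixed month and is not anchored to the previous interview, so a late or missed visit leaves days of the 84-day primary outcome unasked

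*Protocol*

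**What the plan says.** The section on outcome measures and data analysis defines the primary outcome as "the total number of days of crack-cocaine use during the 12 weeks study period (range: 0 – 84 days").

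The Assessments section sets the schedule: "study assessments will take place at baseline, and 4, 8, and 12 weeks after baseline". At baseline the instruments include "the Time Line Follow-Back (TLFB, pertaining to cocaine use in the previous month"). For the two middle visits it says "At the 4 and 8 weeks assessment, the TLFB (pertaining to cocaine use in the previous month"). For the last visit it says only "At the 12 weeks assessment, (follow-up versions of) each of these instruments will be administered again, with the exception of the CIDI, MINI and RCQ", so the week-12 recall period has to be inferred from the baseline version.

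On missing data, the protocol says "multiple imputation will be applied for missing interview data".

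Table 1 lists the TLFB at baseline and at weeks 4, 8 and 12. At weeks 4 and 8 the text limits the Addiction Severity Index items to substances other than cocaine. The twice-weekly urine samples belong to weeks 9 to 12. For weeks 1 to 8, the TLFB is therefore the only source of use-days.

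The protocol gives no length of the month in days and no visit window. It does not link one interview's recall to the interview before it.

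**The concern.** The outcome is one unbroken span of 84 days. The recall instruction works backwards from whatever day the interview happens to take place. The two agree only when each visit falls on its planned day. When a visit slips, an assessor who follows the protocol will not ask about the days between the end of the previous window and the start of the current one. When a visit is missed, the next interview still asks about its own month only. The skipped four weeks are then imputed, even though the patient is present and the TLFB is a calendar recall tool.

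This concerns what is collected, not how it is analysed. A statistical analysis plan can remove duplicated days and set rules for building a total. It cannot recover days that no one asked about. The secondary outcome of longest cocaine abstinence is affected too, because a run of abstinence that crosses an unasked gap cannot be measured.

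**Working it through.** **Plan's own figure.** The Power Considerations section gives a difference of 10 days, SD 17, two-sided alpha 0.10 and power 0.80. Then n per group = 2 × (1.645 + 0.842)² × 17² / 10² = 35.7, rounded up to 36. The stated 36 per group reproduces, and nothing below changes it.

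**Length of the month.** Visits are four weeks apart. The key to Table 1 explains its weekly symbol with "Indicates weekly (instead of monthly) registration", so the ordinary four-week column spacing is called monthly. Pregnancy testing is described as monthly and is scheduled at baseline and weeks 4, 8 and 12. The stated maximum of 84 equals 3 × 28. The protocol's own usage therefore supports a 28-day month, and 28 is used here. For week 12 the same look-back is assumed, since none is restated.

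**Coverage.** An interview on day v with a 28-day look-back covers days v − 27 to v. The delay of seven days is an assumption for illustration.

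| Visit days | Windows | Days of 1–84 never asked about | Days asked about twice | Days after 84 included |
|---|---|---|---|---|
| 28, 56, 84 (on time) | 1–28, 29–56, 57–84 | 0 | 0 | 0 |
| 35, 56, 84 (week 4 late) | 8–35, 29–56, 57–84 | 7 (days 1–7) | 7 (days 29–35) | 0 |
| 28, 63, 84 (week 8 late) | 1–28, 36–63, 57–84 | 7 (days 29–35) | 7 (days 57–63) | 0 |
| 28, 56, 91 (week 12 late) | 1–28, 29–56, 64–91 | 7 (days 57–63) | 0 | 7 (days 85–91) |
| week 4 missed | 29–56, 57–84 | 28 (days 1–28) | 0 | 0 |
| week 8 missed | 1–28, 57–84 | 28 (days 29–56) | 0 | 0 |

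One late visit: 7/84 = 8% of the outcome period unasked. One missed visit: 28/84 = 33%.

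**Effect on one patient's total.** Suppose week 4 is late and undated window totals are simply summed. The error is then use in days 29–35 minus use in days 1–7. It lies between −7 and +7 days and is zero for a patient whose use is stable. This is an error in one patient's score, not a shift in a group mean, so it should not be set directly against the planned 10-day difference.

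**How many patients could be affected.** The documents give no missed-visit rate. As an assumption, let each of the three interviews be missed independently with probability p. The chance that week 4 or week 8 is missed and a later interview is attended is (1 − p)[1 − (1 − p)²] + p²(1 − p) = 2p(1 − p). This is 18% for p = 10% and 32% for p = 20%. These values show scale only; they are not estimates for this trial.

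**After the change.** If each look-back starts the day after the last day covered (or on day 1) and is cut at day 84, each of the 84 days is covered exactly once, provided the week-12 interview takes place on or after day 84.

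**The case against.** The strongest reply is that the schedule works as written: a month is four weeks, visits are four weeks apart, and three windows make 84 days. That stands. A reader might infer that a 30- or 31-day month gives 90 or 93 day-slots and totals above the stated maximum. The protocol's own use of monthly and its 0 to 84 range point the other way, so that reading is not supported.

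A reader might also infer that days are counted twice. This would follow only if undated window totals were summed, and no section says they are. The planned longest-abstinence outcome needs day-level data, and with dated days an overlap can be seen and removed. That stands too, but dating the days does nothing for the gaps.

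Nor are the days of a missed interview simply dropped, since multiple imputation is specified for them, and a missed visit duplicates nothing. What remains is that imputation is used where an answer could still be sought.

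Short recall is a defensible choice: asking heavy crack-cocaine users about 56 or 84 days may be less accurate than asking about 28. This is a fair reason to flag back-filled days and test their influence, but not a reason to leave them unasked. Finally, supervised daily dispensing at the treatment site favours attendance, so late and missed interviews may be few. That limits how often the problem occurs, but it also means that patients can usually be reached and asked.

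**Conclusion.** The point holds as a cheap improvement to a stated data-collection rule, not as an error in any figure. On schedule there is no defect. Off schedule, a seven-day delay leaves 7 of 84 days unasked, and a missed week-4 or week-8 interview sends 28 of 84 days to imputation that a later interview could have supplied. These counts rest on a 28-day month and on a week-12 look-back of the same length, which is inferred rather than stated.

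The main effect is lost precision in the primary outcome. A reader might infer that the treatment comparison is biased. The documents do not support that: bias would need visit timing or attendance to differ between dexamphetamine and placebo, and no section gives rates of either. The overall size is therefore unknown.

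**What to change.** In the Assessments section, replace the fixed month at weeks 4 and 8, and state the same rule for week 12:

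- The TLFB covers every calendar day since the last day covered by the previous completed TLFB, or since day 1 if there is none, and is recorded by date.
- Each of days 1 to 84 is scored once; days after day 84 are excluded.
- Multiple imputation is limited to days that no interview covered.
- The baseline window is set at 28 days. This also matters because the Emergency unblinding section bases imputed values on the patient's baseline value, which should refer to a period of the same length.
- Days collected late because an interview was missed are flagged, and the primary analysis is repeated without them.

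The cost is a sentence or two in the protocol and a dated calendar in the case report form. The downside is longer recall for back-filled periods only: up to 56 days if one interview is missed, and up to 84 if both week 4 and week 8 are missed. The sample size stays at 36 per group.

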2004). In addition, the regular supervised prescription regimen may by itself help the patient to structure his daily life. Oral application of sustained release dexamphetamine, with a much slower onset and limited peak effect than crack-cocaine, clearly meets the rationale for substitution treatment. As in any medication study, the primary focus of our study will be on the balance between (potential) benefit and harm produced by the medication, taking into consideration the personal and societal damage associated with continued illicit use of cocaine, in a situation without effective pharmacological treatment options.

STUDY OBJECTIVE

The overall objective of this feasibility study is to investigate the usefulness of sustained release dexamphetamine in the treatment of cocaine dependence, and – dependent upon the results of both this study and the parallel studies of topiramate and modafinil (see Preface) – to yield one or more candidate medications for future investigation in a large-scale confirmatory controlled trial. Specifically, the study aims to evaluate, in crack dependent patients with comorbid heroin dependence, the response to medically prescribed oral dexamphetamine SR (60 mg/day) as an add-on to heroin-assisted treatment, in terms of potential efficacy, acceptance, compliance, safety, and patient satisfaction.

GENERAL STUDY DESIGN

The study will be conducted using a multicenter, double-blind, placebo-controlled, randomized treatment design. Following screening and baseline assessment, eligible patients in a heroin-assisted maintenance treatment program will be randomly allocated (ratio: 1:1) by the collaborating pharmacist to (continued) heroin-assisted treatment plus 12 weeks treatment with placebo (control group; n=36) or to (continued) heroin-assisted treatment plus 12 weeks treatment with sustained release dexamphetamine 60 mg/day (experimental group; n=36). Randomization will be concealed, using a computer-generated randomization list, and will be prestratified by treatment center (4 treatment centers). Study assessments will take place at baseline, and 4, 8, and 12 weeks after baseline. The primary time point at which treatment outcome will be determined is 12 weeks after baseline.

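### A fixed one-month TLFB look-back covers the 84-day primary outcome exactly once only if every visit is on time; it should run from the previous completed interview

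*Protocol*

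**What the plan says.** The Outcome Measures and Data Analysis section defines the primary outcome as "the total number of days of crack-cocaine use during the 12 weeks study period", with a range of 0 to 84.

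The Assessments section sets the visits: "study assessments will take place at baseline, and 4, 8, and 12 weeks after baseline". Table 1 shows the TLFB at all four visits, and no other instrument is named as a source of cocaine days at follow-up. At baseline the TLFB looks back one month. At weeks 4 and 8, "the TLFB (pertaining to cocaine use in the previous month) and the ASI-items pertaining to other substance use will be administered". For the last visit the text is "At the 12 weeks assessment, (follow-up versions of) each of these instruments will be administered again, with the exception of the CIDI, MINI and RCQ", with no separate look-back stated.

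The protocol does not say outright that the three interviews are added together. The Emergency unblinding section points that way, because it speaks of "the observed values of the primary outcome measure (days of crack-cocaine use) during these remaining assessments", that is, of values belonging to individual visits. Missing interview data are to be multiply imputed. The protocol prints no visit window.

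**The concern.** The outcome needs each of 84 consecutive days classified once. A look-back of fixed length, counted back from whatever date the interview takes place, does that only if the interviews are exactly one look-back apart. When a visit slips, the window slips with it. When a visit is missed, the stated window of the next interview does not extend to the uncovered days.

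What is at stake is measurement error and avoidable missing data in the primary outcome. If answers are stored as dated days, the analyst can remove overlaps later. Days that nobody asked about cannot be recovered. Follow-up urine sampling is confined to weeks 9 to 12, so it offers no substitute for days lost earlier. Longest duration of abstinence, a secondary outcome, also depends on an unbroken daily record.

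**Working it through.** **Planned sample size.** Inputs from Power Considerations: difference 10 days, SD 17 days, two-sided alpha 0.10, power 0.80.

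n per arm = 2 × (1.645 + 0.842)² × (17/10)² = 2 × 6.18 × 2.89 = 35.7, rounded up to 36. This reproduces the protocol's figure. Power at 36 per arm is 0.803 (normal approximation).

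**Length of a month.** The protocol does not define it. The footnote to Table 1 calls the four-week columns monthly, the monthly pregnancy tests fall at baseline and weeks 4, 8 and 12, and 84 = 3 × 28. The check therefore uses 28 days.

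**Coverage of days 1 to 84.** An interview on day v covers days v − 27 to v. The 7-day delay is an assumption, because no visit window is given.

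| Visits | Windows | Never asked about | Asked about twice | Outside days 1–84 |
|---|---|---|---|---|
| On time (28, 56, 84) | 1–28, 29–56, 57–84 | 0 | 0 | 0 |
| Week 8 on day 63 | 1–28, 36–63, 57–84 | 7 (29–35) | 7 (57–63) | 0 |
| Week 12 on day 91 | 1–28, 29–56, 64–91 | 7 (57–63) | 0 | 7 (85–91) |
| Week 8 missed | 1–28, 57–84 | 28 (29–56) | 0 | 0 |
| Week 4 missed | 29–56, 57–84 | 28 (1–28) | 0 | 0 |

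A missed week-4 or week-8 visit leaves 28/84 = 33% of the outcome period to imputation.

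**Effect on power.** Suppose window errors add independent noise with SD s to the total, so that the SD becomes √(17² + s²). The values of s are assumptions.

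- s = 2: SD 17.12, power 0.798
- s = 4: SD 17.46, power 0.784
- s = 6: SD 18.03, power 0.761

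**Same cases with a look-back to the last covered day.** Week 8 on day 63 gives windows 1–28, 29–63 and 64–84. Week 12 on day 91 gives 1–28, 29–56 and 57–91, cut at day 84. Week 8 missed gives 1–28 and 29–84. Each covers all 84 days once. The condition is that the last interview takes place on or after day 84. The planning inputs do not change, so the sample size stays at 36 per arm.

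**The case against.** The best defence is that with a 28-day month and punctual visits nothing is wrong: 84 days are asked about, with no gap and no overlap. Punctuality is plausible here, since study medication is taken under supervision at the centre each morning and assessments are paid. When one intermediate visit is late, the days lost and the days doubled are equal in number, so for a steady user the error largely cancels. Missed interviews are already assigned to multiple imputation. Visit windows and removal of duplicates may sit in an analysis plan or interviewer manual that is not shown.

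Most of this stands, and it keeps the point small. It does not remove it. Imputation is planned for missing interviews, whereas a late but completed interview is not missing and its gap is not addressed. No analysis plan can restore days that were never asked about. The look-back is a data-collection rule, and the protocol states it.

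A reader might infer three stronger things that the documents do not support:

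- That three calendar months make about 91 days, an overcount of up to 7 days to set against the planned 10-day effect. The protocol's own use of monthly and the 0 to 84 range point to 28 days. A longer look-back would in any case apply to both arms and would not be a 7-day bias in their difference.
- That better retention on dexamphetamine would make the amount of imputation differ by arm. The background section reports treatment retention in earlier studies. It says nothing about interview attendance in this trial.
- That the 84 days are known to be shifted against treatment. Randomisation follows baseline, but no delay to first dose is stated, so this is only a possibility that a definition of day 1 would close.

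**Conclusion.** The point holds as a modest weakness in data collection. The stated look-back yields a complete 84-day count only when every visit is kept on schedule. One visit a week late costs 7 days never asked about, with 7 asked about twice or taken from beyond day 84. One missed intermediate visit costs 28 of 84 days. For late visits the main consequence is noise, and the power loss is small over the assumed range (0.803 down to 0.761 at worst). There is no evidence of bias between the arms.

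This rests on a 28-day month, on the total being built from the three TLFB interviews (inferred), on week 12 using the same look-back as the other visits (none is stated), and on a 7-day delay chosen for illustration. The protocol gives no figures on how often visits would be late or missed.

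**What to change.** In the Assessments section, replace the one-month look-back at weeks 4, 8 and 12 with: *every calendar day since the last day covered by the previous completed TLFB, back to study day 1 if needed*. The baseline look-back can stay. Record the answers as dated days, and define the primary outcome as the count over study days 1 to 84, each day once.

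State which day is day 1. First dose is a natural candidate, because the intention-to-treat population requires at least one dose and Power Considerations refers to use during 12 weeks of treatment. Any delay between baseline and first dose then does not move the 84-day period. Schedule the last interview on or after study day 84.

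The cost is a change of wording and an instruction to interviewers, with no new instrument or visit. The downside is longer recall after a missed visit: 8 weeks if one is missed, 12 weeks if both week 4 and week 8 are missed. A missed final interview would still need imputation. The change should be made before recruitment starts.
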